5.3. Compliance of the therapy conduction

The patient should take the first study drug dose at the Visit 2 day (Week 0). During telephone contact (TC 1, Week 2, Day 0), the Investigator checks the patient's treatment compliance and whether he/she follows the recommendations on the Patient's Diary filling, and, if necessary, conducts an additional conversation with the patient about the proper drug administration and filling out the Patient's Diary. At Visit 3 (Week 4, Day 29), the patient should return all used and unused study drug packagings. The Investigator will check compliance with the recommendations for study drug self-administration at Visit 3 (Week 4, Day 29) based on the results of accounting for the returned study drug and the patient's diary.

The study drug compliance will be calculated at Visit 3 using the formula:

Compliance = (N dispensed. - N returned.) / N calc. x 100%

where N dispensed. = number of tablets/capsules dispensed, N returned. = number of tablets/capsules returned, N calc. = estimated number of tablets/capsules the volunteer was to receive since the previous visit.

The compliance should be within the interval from 80% to 120%.

Confidential Page 51 of 94

5.4. Packing and labeling of the study drugs

The study drug will be packed and marked in accordance with current law and applicable regulatory requirements, in particular, Federal Law # 61-FZ On Circulation of Pharmaceutical products" dd. April, 12 2010.

Label of investigational product is below:

Label of blister (Label 5829-L01)

Protocol no. MESI3001

Kit number: XXXXXX

Packaging batch number: 5829-BB

Tablet batch number: zzzzz

Contents: 10 film-coated tablets Mebeverine+Simethicone, 135 mg+80 mg

Sponsor: Abbott Product Operations AG

Label of secondary pack (Label 5829-L02)

Kit numb	er: XXXXXX
Instruction	ns for use and route of administration: oral use, 1 tablet 3 times a day, before meal
Packaging	g batch number:
Tablet bat	ch number: zzzzz
Not to be	used after: MM/YYYY
Contents:	100 tablets (10 blisters with 10 tablets Mebeverine+Simethicone, 135 mg+80 mg each)
Storage co	onditions: store in a light-protected place at a temperature not above 25°C
Sponsor: A	Abbott Product Operations AG
CRO:	

For registered medication Duspatalin® in standard trade package and standard label additional label will be applied:

Confidential Page 52 of 94

Label of blister (Label 5829-L03)

Protocol no. MESI3001

Kit number: XXXXXX

Packaging batch number:

Contents: 10 tablets Duspatalin® 135 mg

Abbott Product Operations AG

Label of secondary pack (Label 5829-L04)

FOR CLINICAL TRIAL USE ONLY

Protocol no. MESI3001

Kit number: XXXXXX

Instructions for use and route of administration: oral use, 1 tablet 3 times a day, before meal

Packaging batch number:

Not to be used after: MM/YYYY

Contents: 5 blisters with 10 tablets Duspatalin® 135 mg

Storage conditions: at a temperature below $30^{\circ}\mathrm{C}$

Abbott Product Operations AG

CRO:

KEEP OUT OF THE REACH AND SIGHT OF CHILDREN

For registered medication Espumizan® in standard trade package and standard label additional label will be applied:

Label of blister (Label 5829-L05) (simple white label)

Protocol no. MESI3001

Kit number: XXXXXX

Packaging batch number:

Contents: 25 capsules Espumisan® 40 mg

Abbott Product Operations AG

Confidential Page 53 of 94

Label of secondary pack (Label 5829-L06) (simple white label)

FOR CLINICAL TRIAL USE ONLY
Protocol no. MESI3001

Kit number: XXXXXX

Instructions for use and route of administration: oral use, 2 capsules 3 times a day, after or before meal

Packaging batch number:
Not to be used after: MM/YYYY

Contents: 1 blister with 25 capsules Espumisan® 40 mg

Storage conditions: store at a temperature below 30°C

Abbott Product Operations AG

CRO:

5.5. Accounting of the study drug

KEEP OUT OF THE REACH AND SIGHT OF CHILDREN

The Investigator will be responsible for proper accounting registration of the study drugs to provide their proper receiving, storage, distribution and return. The patients will be instructed to return all, both used and unused, packages of the study drugs to the investigational site at Visit 3. The returned materials will be checked, assessed the patient's compliance. In case the patient loses the study drug package, an appropriate note should be written in the source documentation and in the study drugs accountability log.

Upon completion of the study, all remaining study medications (Mebeverine+Simethicone, Duspatalin®, Espumisan®) should be returned to the local depot and destroyed.

5.6. Study drug storage in the study site

The Investigator will be responsible for the storage of the study drug in the study site throughout the entire period of the study. Restricted access and adequate temperature should be provided. Temperature monitoring should be carried out using thermometers, recording the minimum and maximum temperature during the reporting period. The temperature monitoring data should be recorded in the temperature registration log on a regularly basis. Upon the end of the study and the final calculation, the study drug Mebeverine+Simethicone is to be returned to the Sponsor or representatives.

5.7. Concomitant Medication

All the study drugs and concomitant medication including food supplements should be registered in the patient's source documentation and in the electronic Case Report Form (eCRF). The Concomitant Medication also include allowed by the protocol rescue therapy applied to relief intensive pain episodes - drotaverin in a dose of 80 mg 1 - 3 times a day during one day after the

Confidential Page 54 of 94

episode. This includes all medicinal products and food supplements that are not study medication taken by patients at any time during the clinical study. The patient's source documentation and eCRF should contain the name (generic name of the active substance is preferable), dose, intake frequency, route of administration, indications for use (including the underlying disease, associated disease, adverse drug event or preventative treatment), date of the beginning and completion of a corresponding drug administration. Upon the study completion, the concomitant medication continues, a corresponding mark should be entered in the CRF

5.8. Prohibited medications

While taking part in the study, the patients are prohibited to take other study drugs, as well as medicines of the following groups:

- Antibacterial therapy;
- Systemic glucocorticosteroids;
- Treatment for HIV, hepatitis B or C;
- Treatment for HIV, hepatitis B or C;
- Eluxadoline;
- Linaclotid:
- Selective serotonin re-uptake inhibitors;
- Rifaximin;
- Lubriprostone;
- Antispasmodic therapy (including herbal, but excluding drotaverin to relief intensive pain episode in a dose of 80 mg 1 3 times a day during one day after the episode);
- other drugs, herbal or supplements to eliminate intestinal pain and bloating/flatulence, except for those provided by the study protocol;
- Any change in the dietary advise and probiotic drugs therapy (including the drug and dosage regimen).

Drotaverine hydrochloride will be allowed for intensive abdominal pain. Drotaverine administration should be recorder in the patient's diary (including a dosage).

5.9. Restrictions on the patient's diet and physical activity

Patients should maintain a pre-study food intake regimen and diet. There are no special restrictions on the physical activity.

Throughout the entire period of study the patient should use adequate contraceptive methods. Adequate contraceptive methods include:

- o Oral contraceptives or contraceptive patches or
- o Condoms or diaphragms (barrier method) together with a spermicide or
- Intrauterine devices.

6. DESCRIPTION OF THE PROCEDURES

All the study procedures will be conducted in accordance with the requirements of International Conference on Harmonization Good Clinical Practice Guideline (ICH GCP(E6)) and Eurasian Economic Union (EEU), principles provided in Helsinki Declaration, as well as in accordance with the applicable legislation and regulations of the Russian Federation. The Investigator should agree to monitoring, audits and inspections in the study site and provide direct

Confidential Page 55 of 94

access to the study for the Sponsor and representatives thereof, Independent Ethics Committee and regulatory authorities.

6.1. Informed consent

Written Informed consent will be obtained during the screening before any procedures related to the study are performed.

6.2. Patient Registration

6.3. Demographic data and medical history

To assess the eligibility/ non-eligibility of patients, demographic data (gender, age, race) and a complete medical history, including significant acute and chronic diseases and conditions (i.e. menopause), surgical procedures and allergic reactions should be collected. It is also necessary to ask the patient about any hospitalizations/surgical interventions scheduled for the period of study (if applicable). All new diagnoses and conditions identified in the screening should be included in the patient's medical history.

6.4. Physical examination

Physical examination includes an assessment of general appearance, condition of the skin and mucous membranes, neck (including the thyroid gland), eyes, ears, nasopharynx, lungs, heart, abdomen, back, lymph nodes and neurologic status

Any relevant findings from physical examination are to be recorded on the Medical History form in the eCRF (for findings from the screening evaluation that occurred prior to allocation to treatment). Any change versus baseline evaluation data considered to be an AE, should be registered appropriately in the eCRF and source documents.

6.5. Vital signs, height and weight

This examination includes measurement of body temperature in the armpit, blood pressure in a sitting position, heart rate and respiration rate. Assessment of vital signs will be performed after 10 minutes of rest.

Weight and height of volunteer are measured without shoes. Height are measured only at Screening. Index body weight (BMI) is calculated according to the formula:

BMI = weight / height2 (kg / m2).

Changes in the vital signs regarding the data of the initial examination, regarded as AEs, should be recorded accordingly in the primary documentation and in CRFs.

6.6. Electrocardiography

Electrocardiography (ECG) in 12 leads will be performed in a supine position. The Investigator will examine ECG records, evaluate possible abnormalities, and then sign and date the conclusion. Changes on the ECG vs. baseline, regarded as AEs, should be recorded accordingly in primary documentation and in CRFs. The nest ECG parameters will be evaluated: heart rate, RR, PQ, QT, QRS and QT_C.

6.7. Colonoscopy

Colonoscopy will be performed during screening in patients over 50 years of age who do not have a colonoscopy report on the absence of significant pathology in the last 12 months.

Confidential Page 56 of 94

Colonoscopy should be performed after confirmation of the patient's full compliance with other selection criteria. The procedure and the relevant preparation should be performed as per the standards adopted in the medical diagnostic center. The screening and induction period in the case of colonoscopy is to be extended to 3 weeks.

6.8. Numeric range scale (NRS-11)

NRS-11 is a Visual Analog Scale version (Visual Analog Scale for pain). The scale is a horizontal 10 cm line with the numbers from 0 to 10 located on it, where 0 is "no pain/bloating", 10 is "most severe pain/bloating you can imagine". During Visit 1 (screening and run-in period), the Investigator will train the patient to select a number from 0 to 10 that corresponds to his/her worst pain in the last 24 hours and the greatest bloating/flatulence. Abdominal pain and bloating/flatulence according to the NRS-11 scales will be evaluated at the screening visit, then daily throughout the screening/run-in and study treatment periods (in the Patient's Diary). The Patient's Diary is to be returned to the Site at Visit 3 (Week 4) and stored along with the primary patient's documents. The Investigator should enter the diary data into the eCRF. The baseline parameters of abdominal pain intensity and bloating/flatulence severity for the inclusion criteria assessment will be determined as the average daily NRS-11 scales scores 7 days before randomization (last week of the run-in period).

NRS-11 scales for abdominal pain and bloating/flatulence are provided in Appendix 2.

6.9. Bristol Stool Chart (BSC)

[figure not shown]
Classification of stools according to the BSC is easily understood by patients and makes it possible to quickly identify the nature of stool disorders. In accordance with BSC, hard stool includes types 1 and 2, loose stool—types 6 and 7 (Table 5)

At Visit 1 (Week -1), the Investigator will train patients to assess stool consistency using BSC. Assessment of stool consistency starts at Visit 1, then it is performed for every bowel movement daily until Visit 3 (Week 4).

Confidential Page 57 of 94

Table 5. Bristol Stool Chart.

Bristol Stool Chart

6.10. Quality of life evaluation using the IBSQOL questionnaire

Patients will be asked to evaluate the quality of life using the IBSQOL questionnaire at baseline at Visit 2 (Week 0) and at the end of the study treatment at Visit 3 (Week 4). A sample questionnaire is provided in Appendix 3.

6.11. Laboratory parameters

All laboratory tests under the protocol will be performed at the study sites local laboratories as per the approved standards. Testing for faecal calprotectin will be performed in the local laboratory or central laboratory (if test is not performed or delayed in local laboratory) if there is no result in 1 month before screening. Women of child-bearing potential will undergo a pregnancy strip test (including less than 2-year postmenopause).

Before the study start, the local and central laboratories will provide the necessary certificates and laboratory standards. The laboratory is responsible for providing laboratory reports to the study sites. The Investigator will analyze the results of laboratory tests as per standard clinical practice.

The required laboratory tests will be performed during visits in accordance with the study procedures schedule (TableTable 1). The table below (TableTable 6) provides laboratory parameters to be evaluated in the clinical study. Clinical relevance of the values outside the normal range (or abnormal results) is to be evaluated by the Investigator.

Confidential Page 58 of 94

Hematology		Biochemistry tests	3	Urinalysis	Feces	Serology
	General	Liver function	Renal		analysis	
			function			
Hemoglobin	Glucose	Total bilirubin	Blood Urea	General	Fecal	Anti-HIV
Hematocrit	Total	Direct bilirubin	Nitrogen	properties: color,	calprotectin	antibodies
Red blood cells	protein	Alkaline	Serum	transparency,		Anti-HCV
White blood	Sodium	phosphatase	creatinine	specific gravity,		HBsAg
cells	Potassium	ALT		pH, protein,		
Neutrophils *	Chloride	AST		glucose, bilirubin,		
Lymphocytes *		GGT		urobilinogen,		
Monocytes *				ketone bodies,		
Eosinophils *				nitrites,		
Basophils *				hemoglobin		
Platelets				Sediment		
				microscopy:		
				epithelium, red		
				blood cells, white		
				blood cells,		
				cylinders,		

Table 6Laboratory tests

Abbreviations: ALT - alanine aminotransferase, AST - aspartate aminotransferase, GGT - γ -glutamyltransferase; HIV - human immunodeficiency virus, Anti-HCV - antibodies to hepatitis C virus, HBsAg - surface antigen of hepatitis B virus.

bacteria, salts

The Investigator must review the laboratory report, evaluate possible abnormalities, and then sign and date the conclusion. Hematology (including absolute values of leukocyte formula) and blood chemistry results should be transferred into eCRF.

Urinalysis results has to be accessed as normal/abnormal registered into eCRF. Clinical significance should be also evaluated. Clinically significant laboratory abnormalities should be recorded as AE. Laboratory reports should be kept with primary patient documentation.

6.12. Requirements for Collecting, Recording and Reporting of Adverse Events

Each subject is to be evaluated at every visit. Should any AE be identified at termination visit, the investigator will continue to follow the subject as described in section 6.12.1.6.

The reference safety information of Mebeverine+Simethicone, Duspatalin® and Espumisan® for the expectedness assessment is contained in the Investigators' Brochure, Instructions for medical use and section 1.5.3.

Investigator will be notified by Sponsor's representative in case any updates of IB or comparators labels (Instructions for medical use) become available.

6.12.1. Adverse events

6.12.1.1. Definition of Adverse Event

Any untoward medical occurrence in a patient or clinical investigation subject administered a pharmaceutical product and which does not necessarily have a causal relationship with this treatment. An AE can therefore be any unfavorable and unintended sign (including an abnormal laboratory finding, for example), symptom (including an AE occurring from drug abuse, an AE occurring from drug withdrawal and any failure of expected pharmacological action), or disease temporally associated with the use of a pharmaceutical product, whether or not considered related to the pharmaceutical product.

Confidential Page 59 of 94

An elective surgery/procedure scheduled to occur during a study will not be considered an adverse event if the surgery/procedure is being performed for a pre-existing condition and the surgery/procedure has been pre-planned prior to study entry. However, if the pre-existing condition deteriorates unexpectedly during the study (e.g., surgery performed earlier than planned), then the deterioration of the condition for which the elective surgery/procedure is being done will be considered an adverse event.

6.12.1.2. Recording of Adverse Events

Any AE should be recorded on the Adverse Events form in the eCRF and source documents. In order to avoid vague, ambiguous or colloquial expressions, the AE should be recorded in standard medical terminology rather than the subject's own words. Whenever possible, the Investigator should group together into a single term signs and symptoms which constitute a single diagnosis.

The existence of or change in an AE may be concluded due to the necessity to administer a concomitant medication, from a spontaneous report of the subject, from the physical examination or from special tests like laboratory assessments or other study specified tests (source of AE).

For each subject that has signed the informed consent and prior to study drug allocation at any dose any change to medical status should be recorded in patient's medical file in accordance to local requirements and the medical history eCRF only.

Any change to medical status, which occurs after study drug allocation at any dose in the specified study AE collection period will be handled as an (S)AE.

For each subject that has signed the informed consent but does not qualify for allocation to treatment, i.e. Screen Failure, any change to medical status (from the time of ICF signature until determination of non-qualification for the study) should be recorded in patient's medical file according to local requirements. The related medical status change information will not be reviewed by Abbott or delegated staff, and will not qualify as a study (S)AE.

The post-therapy AE collection period is defined as 30 days after the subject's termination of study drug after the subject's termination of study drug (collection of (S)AEs should be passive in this period unless otherwise specified)

Each AE is to be evaluated for duration, severity, seriousness and causal relationship to the investigational drug. The action taken with study drug, the concomitant treatment/therapy introduced and the outcome as well as whether the event led to study termination will also be recorded.

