6.12.1.8. Reporting Serious Adverse Events

Any SAE (fatal or life-threatening SAE and other SAEs), whether or not related to the study drug, must be reported immediately within 24 hours of the investigator's awareness of the event by telephone, faxing and email the appropriate SAE forms to the following numbers:

Study Medical Monitor

After office hours, the emergency telephone number is:

If a subject should become pregnant during the study, the event will be reported within 1 day of the investigator's knowledge of the pregnancy.

If pregnancy occurs in a subject from the time of ICF signature who does not qualify for allocation to treatment, i.e. Screen Failure, the pregnancy should be recorded in patient's medical file only, in accordance to local requirements. The pregnancy related medical status change information will not be reviewed by Abbott or delegated staff. The pregnancy will not qualify as a study (S)AE.

If pregnancy occurs in a subject from the time of ICF signature who is not disqualified for allocation to treatment, the pregnancy should be recorded in patient's medical file in accordance to local requirements and in Abbott's pregnancy from. The pregnancy related medical status

Confidential Page 62 of 94

change information will be reviewed by Abbott or delegated staff. The pregnancy will not qualify as a study (S)AE.

The pregnancy evolution and outcome, i.e., the health status of the newborn, is to be reported on the Pregnancy Outcome Form

Pregnancy in a study subject is not considered an adverse event. However, the medical outcome of an elective or spontaneous abortion, stillbirth, ectopic pregnancy or congenital anomaly is considered a SAE and must be reported to within 24 hours of the investigator becoming aware of the event and followed-up as described in Section 6.12.2

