7. STUDY PROCEDURES

7.1. Screening and run-in period (Visit 1, Week – 1, Day -7)

Visit window day -21....-7

- The procedure for obtaining the informed consent
- Patient Registration
- Collection of demographic data, medical history and concomitant medication data
- Physical examination
- Assessment of vital signs
- Measuring height, weight, BMI
- Abdominal pain intensity on the NRS-11 scale evaluation (worst pain for the latest 3 months)
- Bloating/Flatulence intensity on the NRS-11 scale evaluation (worst bloating episode for the latest 3 months)
- ECG
- Blood sampling for safety laboratory tests (hematology and blood chemistry, tests for HIV, hepatitis B and C)
- Urine collection for urinalysis
- Feces sampling for Fecal calprotectin analysis (if there is no result in 1 month before screening)
- The urine pregnancy test is carried out on women with child-bearing potential (including women in the menopausal period of less than two years)

Confidential Page 64 of 94

¹ Week -3, Day -21 in case of colonoscopy

- Assessment of inclusion/non-inclusion criteria
- Patient diary dispense
- Colonoscopy should be performed in patients over 50 years of age who do not have a colonoscopy report on the absence of significant colon pathology in the last 12 months who meet all inclusion/exclusion criteria (excluding Inclusion Criteria 5 and 6 that are to be evaluated at a randomization visit). Colonoscopy should be performed not later than 10 days before the randomization visit.

Patient questionnaires, tests, and scales should be completed according to the adopted clinical practice by the certified trained member of the Site study team before dosing.

In case of ambiguous or controversial results of laboratory tests, a single repeated test (retest) may be performed, as agreed with the Sponsor or its representative.

Patients that do not meet all inclusion/exclusion criteria will not be included in the study. Patients not enrolled in the study due to conditions which may be corrected may be re-screened one time, as agreed upon with the Sponsor or its representative.

From this date intake of drugs prohibited by the protocol are not allowed. Intake of drotaverin in a dose of 80 mg 1-3 times a day will be allowed to stop intensive pain episode during one day after the episode.

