7.2. Treatment period

7.2.1. Randomization (Visit 2 Week 0, Day 1).

- Assessment of AE and concomitant medication
- Measuring, weight, BMI
- Assessment of vital signs
- Abdominal pain and bloating/flatulence intensity on the NRS-11 scale evaluation
- Patient diary assessment (Including stool consistency in line with the Bristol stool scale, stool frequency, drotaverine intake and menstrual bleeding days)
- Assessment of inclusion/non-inclusion criteria
- Randomization
- Evaluate the quality of life (IBSQOL questionnaire)
- Study drug dispense

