4.3 Safety analysis

The Safety subject sample will be used for the analysis of the safety data. In addition to this, three treatment groups will be used: "Mebeverine+Simethicone fixed-dose combination", "Espumisan® (simethicone)" and "Duspatalin® (mebeverin)".

The gap period is 7 days for adverse events, 7 days for vital signs, laboratory measurements and concomitant medications.

The following dictionaries are used for coding of medical terms:

Medical term	Dictionary	Version
Concomitant medications	WHO DDE	March 2020, or later
Adverse events	MedDRA	23.1
Medical histories	MedDRA	23.1

Treatment Emergent Adverse Events

An AE that starts during a unique treatment or that already exists before the start of that unique treatment but worsens during the treatment or post-treatment period (if no longer than 7 days after last dose of respective treatment) will be considered as treatment emergent for that unique treatment.

The following unique treatments are distinguished: Mebeverine + Simethicone, 135 mg+80 mg, three times a day; Duspatalin 135 mg three times a day; Espumisan, 80 mg (2 capsules 40 mg) three times a day. AEs will be reported on a per-subject basis, i.e., counting subjects rather than events. This means that if a subject suffers the same AEs repeatedly during the applicable study or treatment period, the event will be counted only once for that period. Repeated events per subject will be summarized according to the following rule: if a subject suffered the same AE more than once, the event will be assigned the worst severity, the closest relationship to the study drug and the earliest starting date. Only treatment emergent AEs (TEAE) will be reported. In the listings, however, all occurrences of the AEs will be presented.

For each unique treatment, TEAES will be summarized by MedDRA primary system organ class (SOC), high level term (HLT) within primary SOC and preferred term (PT) within HLT and primary SOC. Severity and drug-event relationship of adverse events are summarized separately.

In the listings, all occurrences of AEs will be presented together with all relevant information from the eCRFs. In addition, TEAEs will be flagged. Start and end day of the AE and the day of last dose of study drug will be also presented, relative to the start day of the treatment under which is started or worsened and relative to start of any study drug.

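### Serious events between consent and study drug allocation, including those linked to the trial's own screening colonoscopy, are kept out of SAE handling, and the AE schedule contradicts that rule

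*Protocol*

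**What the plan says.** Protocol section 6.12.1.2 draws the line at allocation of study drug. For a consented patient, "prior to study drug allocation at any dose any change to medical status should be recorded in patient's medical file". The rule then closes off every other destination, the AE form among them, by requiring that this be done "in accordance to local requirements and the medical history eCRF only". Handling as an (S)AE is reserved for "Any change to medical status, which occurs after study drug allocation at any dose in the specified study AE collection period". For a patient who fails screening, the event goes into the site's own file, and the information "will not be reviewed by Abbott or delegated staff, and will not qualify as a study (S)AE". Sections 6.3 and 6.4 follow the same routing for conditions and findings at screening.

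Other places start earlier or give no start. Table 1 marks adverse events at Visit 1 and Visit 2. Section 7.2.1 opens its Visit 2 list with "Assessment of AE and concomitant medication", ahead of randomization and dispensing. SAP section 6.1.5 lists adverse events at Screening, referenced to the consent date. Section 7.1, the Visit 1 procedure list, has no AE assessment. Section 6.12.1.8 reads "Any SAE (fatal or life-threatening SAE and other SAEs), whether or not related to the study drug, must be reported immediately within 24 hours" and names no date from which this applies.

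Two exposures fall before allocation. Section 7.1 states: "Colonoscopy should be performed in patients over 50 years of age who do not have a colonoscopy report" from the last 12 months. The same section permits drotaverine for intense pain from Visit 1.

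**The concern.** A trial that requires an invasive procedure to establish eligibility should be able to see serious harm from it. Under section 6.12.1.2 as written, a hospital admission after the screening colonoscopy, or a serious reaction to drotaverine in the run-in, is not a study SAE. If the patient then fails screening, the sponsor never reviews it, so a pattern across about 45 sites could go unnoticed. The SAP provides no other safety body: sections 4.5 and 4.6 mark both the data safety monitoring board and the safety management team as not applicable.

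Sites also face a practical difficulty. The schedule has them assess AEs at screening, while the recording rule gives them no AE form on which to enter the result. Different sites may resolve this differently, which would make pre-treatment safety data incomparable between sites.

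**Working it through.** The plan states no figure for this point, so the check sets the sections side by side.

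**1. The window.** Visit 1 is at Day -7, or as early as Day -21 when a colonoscopy is needed (Table 1, section 7.1). Allocation and first dose are both planned for Visit 2, Day 1 (sections 5.2 and 5.3). The window is therefore 7 to 21 days. The written boundary is allocation rather than first dose, but on the planned schedule the two differ by hours at most.

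**2. What the trial adds in that window.** Colonoscopy must take place at least 10 days before randomization (section 7.1), so the procedure and at least its first 10 days of aftermath lie wholly before allocation. Drotaverine is available from Visit 1; section 3.8.1 calls its side effects rare and includes hypotension, palpitation and allergic reactions among them.

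**3. Tracing one event.** Take an inpatient admission after the colonoscopy, which meets a seriousness criterion in section 6.12.1.7.

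| Patient's later status | Where the event goes | Sponsor sees it? | SAE status, 24-hour report? |
|---|---|---|---|
| Randomised | Site file and medical history form (6.12.1.2); tabulated and listed under SAP 4.3.2 | Yes, as medical history | No |
| Screen failure | Site file only (6.12.1.2) | No | No |

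The second row needs no unusual circumstances. Inclusion criteria 5 and 6 are judged at the randomization visit, after the colonoscopy (section 7.1), so a patient can have the procedure and then fail screening on symptom scores alone.

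**4. The schedule against the rule.**

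| Place | AE collection before allocation? |
|---|---|
| 6.12.1.2 | No |
| 7.1 (Visit 1 list) | Not listed |
| Table 1, Visit 1 | Yes |
| SAP 6.1.5, Screening | Yes, from the consent date |
| 7.2.1 (Visit 2 list) | Yes, listed before randomization |
| 6.12.1.8 | No start date given |

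The conflict between 6.12.1.2 and the screening entries in Table 1 and SAP 6.1.5 is direct. Section 7.1 agrees with 6.12.1.2 and so also disagrees with Table 1.

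**5. Size.** Planned screening is up to 665 and planned randomization is 465, so 665 - 465 = 200 expected screen failures (200/665 = 30%). This is the number whose events would be outside sponsor review. It is not the number having a colonoscopy. That number cannot be derived, because the documents give neither the age distribution nor the share with a recent report.

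**The case against.** The strongest reply is that 6.12.1.2 is a scope rule and 6.12.1.8 a reporting rule, and that the two are compatible: only events that count as (S)AEs need reporting within 24 hours. The definitions lend support. Section 6.12.1.1 speaks of a subject given a pharmaceutical product, and 6.12.1.7 ties seriousness to a dose. A purely procedural complication before any drug fits poorly, although drotaverine is a pharmaceutical product. This stands. A reader might infer that the plan breaches its own 24-hour rule; the documents show only that the rule has no start date, so the conflict depends on how it is read.

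A second reply is that Visit 2 is itself the allocation day, so an AE entry there need not oppose the rule. This has some force, but the assessment is listed before randomization, when the only period to ask about is the run-in. The screening entries remain in conflict either way.

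A third is that the events are not lost for randomised patients. This is correct: they reach the sponsor through the medical history form and its listing.

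A reader might also infer that the SAP's rule for an event that "already exists before the start of that unique treatment but worsens during the treatment" cannot be applied to run-in events. The documents do not support that. Section 6.12.1.2 treats any change after allocation as an (S)AE, so the worsening is recorded on treatment with its own severity. Whether the medical history form holds a severity grade cannot be seen.

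Finally, section 9.2 states that all subjects had been recruited by Amendment 1, so new wording captures nothing prospectively. This changes the remedy but does not remove the defect.

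**Conclusion.** The point holds in this form: section 6.12.1.2 excludes every event between consent and allocation from (S)AE handling, and excludes screen failures' events from sponsor review. It makes no exception for serious events or for those linked to the required colonoscopy or permitted drotaverine. It contradicts Table 1 and SAP section 6.1.5 directly, and sits badly with section 7.2.1.

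The consequence differs by patient. For those randomised, SAE status and rapid reporting are lost, but the record is not. For screen failures, planned at about 200, nothing reaches the sponsor. It would be wrong to conclude that about 200 patients are exposed to colonoscopy: section 6.7 reserves the procedure for those who meet the other criteria, and it applies only over age 50 without a recent report.

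The conclusion rests on the readable text. The protocol's administrative sections on investigator duties and monitoring are not available, and the local requirements that 6.12.1.2 mentions are not described; either could add a reporting route. The efficacy analysis is unaffected. The matter should be corrected because it concerns oversight of harm from a procedure that the trial itself requires.

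**What to change.** Reconcile protocol sections 6.12.1.2, 6.12.1.8, 7.1, 7.2.1 and Table 1 with SAP section 6.1.5 by stating one rule. From consent to allocation, including for screen failures:

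- all SAEs, and all AEs judged related to a protocol-required procedure or to rescue medication, are recorded on the AE form;
- those that are serious are reported under 6.12.1.8, with consent given as the start date;
- they appear in a separate pre-treatment listing and stay out of the treatment-emergent tables.

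Other pre-allocation changes can remain in medical history. Sponsor review from consent already has a precedent: section 6.12.1.8 requires it for pregnancy in patients not yet disqualified.

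Because recruitment had finished by Amendment 1, this trial also needs a single query to sites before database lock, asking for serious or procedure-related events before allocation, screen failures included.

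The cost is that limited retrospective query at about 45 sites, the changed wording, a few more SAE reports and one listing. No visit or procedure is added.
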